## 11 STATISTICAL CONSIDERATIONS

#### 11.1 Method of Randomisation

Once consent has been obtained, participants shall be randomised on a 1:1 basis including the participating site as a stratification factor. Randomisation lists shall be produced by the trial statistician at the LCTC using randomly permuted blocks with separate lists created for each stratification factor. Lists shall be created using Stata (version 15 or above) using the add-on package 'ralloc'.

#### 11.2 Outcome Measures

#### **11.2.1 Primary**

- 1. Recruitment rate will be measured by the:
  - i. Total number of patient participants randomised per month, and
  - ii. Ratio of successful recruitment to eligible patients approached.

## 11.2.2 Secondary

- 1. Adherence to the protocol will be measured by:
  - i. the number of minor (e.g. visit time-point violation) or major (e.g. violation of inclusion criteria) protocol deviations collected on a patient participant and site level. (The definitions of minor and major protocol deviations will be in accordance with LCTC categorisations that will be allocated to each deviation by the CI after assessment of the details)
  - ii. the percentage of patients in each arm that were accidentally unblinded
- 2. Trial withdrawal rate at 6 weeks and 3-6 months will be measured using the total number of patients randomised in the study. In addition, withdrawal rates will be presented by trial withdrawal reasons and withdrawal stage for both arms.
- 3. Patient participant population characteristics will be measured by collecting the following information:
  - i. Age
  - ii. BMI
  - iii. Proportion of missing data
  - iv. Loss to follow up
- 4. Clinical and patient reported data will be measured by collecting the following information:
  - i. Patient participant-reported outcomes including change in OHS, FJS, WPAI-SHP, SAPS score and quality of life measured using the EQ-5D-5L™ at 6 weeks and 3-6 months
  - ii. Revision rate, defined as the number of patient participants needing Revision arthroplasty within 3-6 months of surgery
  - iii. Infection rate, measured as the rate of re-operation for infection within 3-6 months of surgery
  - iv. Length of stay, measured in hours
  - v. Operation time, measured in minutes

**IRAS Ref: 271885** Page 50 of 89

- vi. Incidence of treatment cross over during surgery
- vii. Incidence of intra-operative surgical complications, the proportion of patient participants experiencing greater than grade III severity will be measured and reported according to Clavien Dindo classification system^24.
- viii. Incidence of postoperative surgical complications, the proportion of patient participants experiencing greater than grade III severity will be measured and reported according to Clavien Dindo classification system^24.
- 5. Completeness of the EQ-5D-5L™ and Healthcare Resource Use Survey will be measured by using the follow methods:
  - i. Descriptive statistics will be used to assess the frequency of missing data for the EQ-5D-5L™ and Healthcare Resource Use Survey.
  - ii. Any patterns in missing data will be identified through the use of descriptive statistics

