#### 7.3 Randomisation

Randomisation shall occur pre-operatively once the patient has been deemed eligible for the study, provided written informed consent and their baseline procedures completed. The randomisation sequence is pre-determined by LCTC, see section 11.1 for further details.

**IRAS Ref: 271885** Page 39 of 89

The randomisation will be processed using REDCap, a commercially available on-line research database system, and will be processed by the research team at the recruiting site. It should be completed as soon as possible for the purposes of operation list planning and implant procurement, and must be no later than the day prior to surgery. The only caveat to this deadline is for patients who will not be consented until the day of their surgery, in which case randomisation should be completed as soon as it is possible to do so.

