## 7.6 3-6 month post-op

Patient participants will be required to complete their PROMS questionnaires and healthcare resource use survey between 3 and 6 months postoperatively (from date of

**IRAS Ref: 271885** Page 40 of 89

surgery). This follow-up period will be dictated by the remaining duration of the study. All patient participation activity is expected to be completed by the end of October 20201. See the table below.

Month of Operation	Follow-up time point	Follow-up duration
January '21	July '21	6 months
February '21	August '21	6 months
March '21	September '21	6 months
April '21	October '21	6 months
May '21	October '21	5 months
June '21	October '21	4 months
July '21	October '21	3 months

PROMS questionnaires and a healthcare resource use survey will be sent in the post for the patient participant to complete. The accompanying cover letter will advise that the Oxford Hip Score is to be completed first, others are shown in a recommended order of completion of most recent recall period:

- Oxford Hip Score
- EQ-5D-5LTM
- Self-Administered Patient Satisfaction scale
- Forgotten Joint Score
- Work Productivity and Activity Impairment-Specific Health Problem
- Healthcare Resource Use Survey

A member of the hospital research team will contact the patient participants by phone before distribution to inform them of the upcoming postal questionnaires. The questionnaires should be posted early enough that the patient participant is in possession of them at the required 3-6 month post-operative date.

Patient participants will also be asked about any return to theatre required and any unanticipated contact with the surgical team or GP regarding the surgery.

The earliest that this data can be collected is 4 months postoperatively and the latest time is 8 months. Completion of these questionnaires outside of these parameters will be recorded as protocol deviations but will not affect the patients continuing participation in the trial.

Details on how and when to return the questionnaires are included within the covering letter.

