## 7.9 Procedures for assessing Efficacy

Clinicians will use their usual criteria to determine if an intervention is deemed to have failed clinically and if a re-intervention is necessary. This information will be recorded in the patient participant's notes and on the appropriate CRF. The nature of any re-intervention will be at the discretion of the treating clinician who will use their skill, knowledge and expertise to determine the most appropriate treatment.

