#### 9 BLINDING

To prevent bias in the completion of their answers to PROMS questionnaires, it is key that for the duration of their time on the study, i.e. until the 3-6 month post-operative PROMS questionnaires have been completed, a patient participant remains blinded to the type of implant they have received.

It is acknowledged that it is impossible to blind the surgeon, operation team and other healthcare professionals to the type of implant the patient participant received. Members of the research team being aware of the implant type will have no bearing on the outcomes of the study, however every effort must be made to ensure that patient participants remain blinded to the type of implant they received, at least until a patient has completed their 3-6 months post-operation PROMS questionnaires. These efforts must include, but are not limited to:

- Excluding members of the research team from correspondence that reveals the randomised allocation of the type of implant.
- Ensuring the patient is provided with and wears ear plugs during surgery.
   Alternatively, they can provide their own device and earphones to listen to music etc. instead (earphones do not have to be to any particular standard or specification, e.g. 'noise cancelling').
- Ensuring post-operative documentation that the patient or research team may have access to (e.g. discharge letter, physiotherapy referral) do not refer to the type of implant used.
- Marking/Annotating the operation notes to advise the reader to not disclose or allude to the type of implant used when in communication with the patient or research team.

If a patient participant does accidentally becomes unblinded to the type of implant they have received, the relevant CRF will need to be completed and returned to LCTC. Such occurrences will be recorded as protocol deviations but will not affect the patient continuing participation in the trial. Corrective and preventative actions must be undertaken locally to prevent similar events leading to unblinding to other patients.

If a member of the research team accidentally becomes unblinded to the type of implant patient receives, it does not have to be reported to LCTC. Corrective and preventative actions must however be undertaken locally to prevent the patient becoming aware, e.g. remove/reduce interaction between the member of the research team and the patient participant if possible.

**IRAS Ref: 271885** Page 47 of 89

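### Unblinding outcome 1(ii) counts only accidental cases that reach an event-triggered CRF; with no scheduled question listed, it probably understates how many patients knew their implant at the PROMs

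*Protocol*

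**What the plan says.** Section 11.2.2 lists, as the second measure under adherence to the protocol, "the percentage of patients in each arm that were accidentally unblinded". It is the only quantitative blinding measure in the document.

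Section 9 explains why the blind matters: to prevent bias in the PROM answers, "it is key that for the duration of their time on the study" the patient stays unaware of the implant type, up to completion of the 3-6 month PROMs. On data capture it says: "If a patient participant does accidentally becomes unblinded to the type of implant they have received, the relevant CRF will need to be completed". Such events are also recorded as protocol deviations.

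For the final assessment, section 7.6 says "PROMS questionnaires and a healthcare resource use survey will be sent in the post for the patient participant to complete". The planned staff contact is a call made beforehand to announce the pack: "A member of the hospital research team will contact the patient participants by phone before distribution". The enquiry listed besides the questionnaires is: "Patient participants will also be asked about any return to theatre required and any unanticipated contact with the surgical team or GP".

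Section 7.5 (6 weeks) lists the PROMs, adverse events of special interest, antibiotic prescriptions and unplanned contacts. Table B in section 7.8 lists the PROMs, the resource use survey, routine surgical data and serious events or incidents. None of the three places lists a question about knowledge of the implant.

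**The concern.** The full trial is to have a patient-reported functional score as its primary outcome (section 2.2) and is described as blinded (section 4.1). Whether patients can be kept unaware of their implant until that score is recorded is something a feasibility study can usefully show, and item 1(ii) is where a reader will look for it.

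As defined, the item has two gaps:

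- **Capture.** A case counts only if a staff member learns of it and completes a form, and nothing scheduled prompts that discovery.
- **Definition.** The word *accidentally* leaves out a patient who was told on purpose, although that patient answers later PROMs just as unblinded.

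A low figure could then mean that the blind held or that nobody recorded the failures, and the data could not tell the two apart. The count also feeds the feasibility judgement, because unblindings are deviations and section 11.5 requires that there be no serious issues with protocol deviations.

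**Working it through.** The protocol states no unblinding rate, target, precision or capture rate, so there is no figure to reproduce. The check is first textual, then a range under stated assumptions.

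**Step 1: where could a case be picked up?**

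| Contact | What is listed | Question on implant knowledge? |
|---|---|---|
| 6 weeks (7.5) | PROMs, adverse events, antibiotics, unplanned contacts | None listed |
| Call before the final pack (7.6) | Announces the questionnaires | None listed |
| 3-6 months (7.6) | Postal PROMs and survey, return to theatre, unplanned contacts | None listed |
| Schedule, Table B (7.8) | As above, plus surgical data and serious events | None listed |
| Unblinding CRF (9) | Completed when an accidental unblinding occurs | Triggered by the event; no detection method stated |

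A statistical analysis plan cannot repair this, because it cannot analyse answers that were never collected.

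**Step 2: direction.** Let p be the true proportion of an arm who know their implant by the final PROMs, and s the share of those who end up on a CRF and meet the accidental definition. The expected reported proportion is p × s. Unless there are false reports, this cannot exceed p, and it falls short whenever s is below 100%.

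**Step 3: possible size.** Neither p nor s is in the documents. I assume p from 5% to 30% and s from 25% to 100%. Arm size is 40/2 = 20 (section 4.1: 40 patients, 1:1). The chance that an arm shows no case is (1 − p × s)^20. Each cell gives the expected reported rate, then that chance.

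| True p | s = 100% | s = 75% | s = 50% | s = 25% |
|---|---|---|---|---|
| 5% | 5.0%; 0.358 | 3.8%; 0.466 | 2.5%; 0.603 | 1.2%; 0.778 |
| 10% | 10.0%; 0.122 | 7.5%; 0.210 | 5.0%; 0.358 | 2.5%; 0.603 |
| 20% | 20.0%; 0.012 | 15.0%; 0.039 | 10.0%; 0.122 | 5.0%; 0.358 |
| 30% | 30.0%; 0.001 | 22.5%; 0.006 | 15.0%; 0.039 | 7.5%; 0.210 |

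For example, with p = 20% and s = 25%, p × s = 5% and 0.95^20 = 0.358. With full capture, 0.80^20 = 0.012.

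**Step 4: precision with full capture.** For no cases in n patients, the exact two-sided 95% upper limit is 1 − 0.025^(1/n). That is 16.8% for n = 20 and 8.8% for n = 40. Sampling error is large even when everyone is asked. Under-capture adds a downward bias that this interval does not cover.

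**The case against.** The strongest defence is that item 1(ii) is a deviation tally. It sits under adherence, next to counts of minor and major deviations. Testing the blind is not among the seven secondary objectives, and the stop/go thresholds rest on recruitment. This stands as a description of where the item sits. It does not change what the percentage will and will not contain, and section 9 itself treats the blind as key.

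Second, staff do have contact with patients. The 6-week visit is to be in person if possible, a call precedes the final pack, and Workstream 2 asks about experiences of randomisation and participation. The CRFs are not shown. So the text supports only that no scheduled question is listed; a reader might infer that nobody will ask, and that goes too far. The interviews are qualitative, cover a sample, usually take place within four weeks of surgery, and are not linked to item 1(ii).

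Three stronger readings are tempting, and the protocol does not support them:

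- **Pre-operative leaks are left open.** Allocation is known early, "for the purposes of operation list planning and implant procurement", and most of the measures named in section 9 concern theatre and later documents. But that list is expressly non-exhaustive, requires every effort, and its item on correspondence revealing the allocation is not confined to the period after surgery.
- **Re-intervention means disclosure.** Section 7.9 says "The nature of any re-intervention will be at the discretion of the treating clinician". That concerns the choice of treatment and says nothing about telling the patient the implant type. Returns to theatre and revisions are collected anyway; what is missing is whether those patients were told.
- **The measure misses most failures.** The documents give no basis for saying what share is missed.

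Finally, asking carries a risk. A question at 6 weeks could lead patients to find out their implant before the 3-6 month PROMs. That objection is sound and shapes the remedy.

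**Conclusion.** The point holds in limited form. Item 1(ii) will give the percentage of patients with a reported accidental unblinding. That is likely to be lower than the percentage who knew their implant when they completed the PROMs, by an amount the documents cannot supply.

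The direction rests on two assumptions: that some cases go unreported or are not accidental, and that false reports are negligible. The table in the working shows what follows from assumed rates and is not an estimate for this trial. With about 20 patients per arm the result will be imprecise in any case, so the gain from the change is a figure that means what it appears to mean, not a precise one.

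This is a modest, inexpensive improvement to a stated secondary outcome. It does not affect the recruitment-based stop/go thresholds.

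**What to change.** 1. Redefine item 1(ii) as the percentage of patients in each arm who knew their implant type by the 3-6 month PROMs, for any reason, with source and date.
2. Collect it with one factual question placed after all the PROMs in the 3-6 month pack only: *Have you been told, or found out, which type of hip socket you received? If yes, when and how?* The date given shows whether the knowledge came before the 6-week PROMs. State how many patients did not return the pack or left the item blank.
3. Keep the unblinding CRF, and report its count beside the new figure, labelled as reported accidental events.
4. Do not add the question at 6 weeks, where it could prompt unblinding before the final PROMs.

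The cost is one more question in an existing pack and a change of wording in section 11.2.2, with matching entries in section 7.6 and Table B. The remaining downside is that the question may arouse curiosity, but placed last it does so after the final assessment that section 9 protects.

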## 7.5 6 weeks post-op

All patient participants will be reviewed in a routine outpatient clinic at 6 weeks postoperatively (from date of surgery). Please also see section 7.12 on contingency planning.

PROMS questionnaires to be completed are listed below. The Oxford Hip Score is to be completed first, others are shown in a recommended order of completion of most recent recall period:

- Oxford Hip Score
- EQ-5D-5L™
- Self-Administered Patient Satisfaction scale
- Forgotten Joint Score
- Work Productivity and Activity Impairment—Specific Health Problem

Data will also be collected Adverse Events of Special Interest; these will primarily be surgical complications, such as but not limited to returns to theatre for dislocation, fracture or wound problems; any prescriptions for antibiotics will be noted and any unanticipated contact with the surgical team or GP regarding the surgery.

The earliest this visit can occur is 3 weeks postop and the latest is 12 weeks postop from the date of surgery. Visits outside of these parameters will be recorded as protocol deviations but will not affect the patients continuing participation in the trial.

Every effort should be made to meet the patient in person during the visit. Should this not be possible the questionnaires should be posted as soon as possible to the patient for their completion. Details on how and when to return the questionnaires are included within the covering letter. (See also section 7.7 Loss to follow-up.)

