#### The following are reportable to LCTC:

- Any Adverse Event of Special Interest (AESI) with a severity grading of 3 or above according to the Clavien Dindo classification system^24 (see table D).
- Any Adverse Device Event that meets the definition of serious (see section 12.5) and is assessed as being related a device (i.e. an implant or bone cement).

No other safety events are required to be reported to LCTC. All safety events (regardless of the requirement to report to LCTC) are to also be recorded and reported as per local policy.

**IRAS Ref: 271885** Page 54 of 89

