## Reporting requirements decision tree:

**IRAS Ref: 271885** Page 55 of 89

Table C	: Adverse Events of Special Interest (in alphabetical order).
Event	
1.	Cerebrovascular accident
2.	Deep infection
3.	Deep Vein Thrombosis
4.	Dislocation of hip (subluxation or dislocation of joint)
5.	Fracture around joint including femoral shaft perforation or fracture, calcar fracture, trochanteric fracture, acetabular (fracture or perforation) or pelvic fracture (intraoperative)
6.	Fracture around joint including trochanteric avulsion, femoral or acetabular or pelvic fracture (postoperative)
7.	Haematoma
8.	Heterotopic ossification of joint leading to pain or stiffness (periarticular calcification or ossification)
9.	Loosening of implants (early or late, change in position of implants, subsidence of implants or tissue reaction/osteolysis)
10.	Myocardial infarction
11.	Nerve injury (temporary or permanent nerve damage including femoral, obturator, peroneal, sciatic)
12.	Organ/Multiorgan failure
13.	Pain from joint
14.	Pneumonia
15.	Pulmonary Embolism
16.	Revision surgery
17.	Superficial infection
18.	Vascular injury (including iliac, obturator and femoral artery injury)
19.	Wear or fracture or fatigue fracture of implants

**IRAS Ref: 271885** Page 56 of 89

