## 12.4 Assessment of Severity

Important Note: A distinction is drawn between **severe** and **serious**. Severity is a measure of intensity, whereas seriousness is defined using the criteria in Section 12.5. However, any AE's with a severity grading of 4 or 5, according to the Clavien Dindo classification system^24 (i.e. life-threatening or fatal), also meet the criteria of serious.

Table D: Clavien Dindo classification system^24.

Grade	Definition
1	
 
Any deviation from the normal postoperative course without the need for pharmacological treatment or surgical, endoscopic and radiological interventions.
 
Allowed therapeutic regimens are: drugs as antiemetics, antipyretics, analgetics, diuretics and electrolytes and physiotherapy.
 
This grade also includes wound infections opened at the bedside.
 

2	
 
Requiring pharmacological treatment with drugs other than such allowed for grade 1 complications.
 
Blood transfusions and total parental nutrition are also included.
 

3a	Requiring surgical, endoscopic or radiological intervention – not under general anaesthesia.
3b	Requiring surgical, endoscopic or radiological intervention – under general anaesthesia.
4a	
 
Life-threatening complication (including CNS complications*) requiring intermediate care or intensive care management – single- organ dysfunction (including dialysis).
 

4b	
 
Life-threatening complication (including CNS complications*) requiring intermediate care or intensive care management – multi- organ dysfunction.
 

5	Death of a patient.
*brain ha	aemorrhage, ischemic stroke, subarachnoidal bleeding, but excluding

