## 12.8.1 Adverse Events of Special Interest

Any AESI with a severity grade of 3 or higher is to be recorded on the Adverse Events CRF.

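### The outcome named infection rate counts only re-operations for infection, so infections treated with antibiotics alone normally enter no listed safety outcome

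*Protocol*

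**What the plan says.** The only infection outcome in the protocol is item 4(iii) of section 11.2.2: "Infection rate, measured as the rate of re-operation for infection within 3-6 months of surgery". Item 4(viii) of the same list covers post-operative complications, with a severity cut-off: "Incidence of postoperative surgical complications, the proportion of patient participants experiencing greater than grade III severity will be measured and reported".

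Infection is plainly of interest elsewhere. Table C lists deep infection and, as a separate entry, "Superficial infection" among the adverse events of special interest (AESIs). At the 6-week visit (section 7.5) "any prescriptions for antibiotics will be noted and any unanticipated contact with the surgical team or GP regarding the surgery". At 3-6 months (section 7.6) patients are "asked about any return to theatre required and any unanticipated contact with the surgical team or GP", and antibiotics are not named.

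The recording rules are narrower than the list of events. Section 12.3 makes an AESI reportable to the trials centre only "with a severity grading of 3 or above according to the Clavien Dindo classification system", and section 12.8.1 says: "Any AESI with a severity grade of 3 or higher is to be recorded on the Adverse Events CRF". Table D in section 12.4 defines grade 2 as "Requiring pharmacological treatment with drugs other than such allowed for grade 1 complications".

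**The concern.** Intra-operative and post-operative safety is secondary objective 5 in section 2.3. A reader of the results would take a line headed infection rate as the share of patients who had an infection. Under 4(iii), an arm with several infections treated with antibiotics and none re-operated would be reported as 0%. Nothing else in 11.2.2 would normally show those cases. The antibiotic prescriptions, the one 6-week item that points to them directly, feed no outcome in that list.

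**Working it through.** The protocol states no infection rate, so there is no figure of its own to reproduce. The check follows an infection through the rules according to how it was managed.

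| Management of the infection | Grade in Table D | Counted in 4(iii)? | Counted in 4(viii), above grade III? | On the Adverse Events CRF as an AESI (grade 3 or higher)? |
|---|---|---|---|---|
| Wound opened at the bedside | 1 | No | No | No |
| Antibiotics only | 2 | No | No | No |
| Re-operation | 3a or 3b | Yes | No | Yes |
| Life-threatening or fatal | 4 or 5 | Only if re-operated | Yes | Yes |

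Two further routes were checked.

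- **SADE reporting.** Hospitalisation makes an event serious (section 12.5). If the event is also judged related to an implant or the cement, it is reportable as a serious adverse device event (sections 12.3 and 12.6). An antibiotic-treated infection could reach the trials centre this way, but through safety reporting and not through an outcome in 11.2.2.
- **Grade 3 without re-operation.** A radiological intervention for infection, for example, would go on the Adverse Events CRF. Read literally, it would enter neither 4(iii) nor 4(viii).

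Let p be the share of patients with any infection and f the share of infected patients who are re-operated. Item 4(iii) then estimates p × f. This cannot exceed p, and is lower whenever an infection is managed without re-operation. The document gives neither p nor f, so the shortfall p × (1 − f) cannot be derived from it.

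**Illustration on assumed values only.** N = 40 is from section 4.1; p and f are assumptions.

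- Expected patients infected: N × p
- Expected count under 4(iii): N × p × f
- Chance that 4(iii) reports zero: (1 − p × f)^40
- Chance of at least one infected patient: 1 − (1 − p)^40

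| p | Expected infected | Expected count under 4(iii), f = 10% / 25% / 50% | Chance 4(iii) is zero, f = 10% / 25% / 50% | Chance of at least one infected patient |
|---|---|---|---|---|
| 2% | 0.8 | 0.08 / 0.20 / 0.40 | 0.92 / 0.82 / 0.67 | 0.55 |
| 5% | 2.0 | 0.20 / 0.50 / 1.00 | 0.82 / 0.60 / 0.36 | 0.87 |
| 10% | 4.0 | 0.40 / 1.00 / 2.00 | 0.67 / 0.36 / 0.13 | 0.99 |

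Worked cell: p = 5%, f = 10% gives p × f = 0.005 and 0.995^40 = 0.82.

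A zero would also be imprecise. The exact two-sided 95% upper limit for 0/40 is 1 − 0.025^(1/40) = 8.8%.

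**The case against.** The best defence has four parts.

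1. **The definition is stated openly.** Item 4(iii) gives its measure in the same line as its name. A reader might infer that the reported figure would be false. The protocol does not support that: the number is a correct rate of re-operation for infection. Only the name misleads.

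2. **The restriction is deliberate.** Section 12.3 argues that the safety profile of these CE-marked implants is well known and that limited recording harms neither participants nor the aims. Re-operation is grade 3, so 4(iii) matches the AESI threshold and picks up re-operations that 4(viii) would miss. This stands as a reason for limited safety reporting. It is not a reason to call a re-operation rate an infection rate.

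3. **The data for a full infection outcome are not shown to exist.** A reader might infer from section 7.5 that wound problems are recorded as such; there they are an example of a reason for returning to theatre. The antibiotic item names no indication, and nothing shows that infection depth or bedside opening is collected below grade 3. Nor is it right that later antibiotics go wholly unasked: the resource use survey at 3-6 months covers prescribed medicines (section 10.4), though for the economic analysis. All of this stands and limits the fix.

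4. **No decision depends on the figure.** A reader might infer that the full trial would adopt it as its planning risk. No section says so. The stated inputs are recruitment, PROM variability, loss to follow-up, cross-over and the intraclass correlation (sections 2.2 and 11.3). The stop/go rule in section 11.5 rests on recruitment, with randomisation, retention and deviations, and that section rules out formal safety assessment across arms. A broader count would also be imprecise: 2/40 has an exact 95% interval of about 0.6% to 17%. This stands and keeps the weight modest.

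The unseen analysis plan may tabulate antibiotic prescriptions. That would not alter the name and measure that the protocol itself fixes.

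**Conclusion.** The point holds as a labelling defect with a gap behind it. Item 4(iii) is a re-operation rate named as an infection rate. Infections treated with antibiotics or opened at the bedside enter no listed safety outcome, apart from a serious device-related event reported as a SADE or an event reaching grade 4 or 5. The 6-week antibiotic data are used by no outcome in 11.2.2. These statements rest on the protocol's text alone. The direction of the shortfall follows from the definition; its size is unknown, and the probabilities above depend wholly on assumed rates. With 40 patients, descriptive safety reporting and no decision tied to infection, this is a cheap improvement and not a threat to the study's conclusions.

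**What to change.** - Rename item 4(iii) 'Re-operation for infection'.
- Add a descriptive row by arm: the number and percentage of patients with an antibiotic prescription noted up to the 6-week visit. Show prescriptions for a wound or hip infection separately where the indication is recorded, and apply no Clavien Dindo cut-off.
- Do not promise a split by superficial or deep infection or by bedside opening, because the protocol does not show that these are collected below grade 3.

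The cost is a wording change and one table row. The indication may need one extra CRF field, and some prescriptions will be for unrelated reasons, so the overall row must not itself be called an infection rate. The change concerns reporting only and alters no treatment or clinical rule.

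### Intra-operative complications are counted only through a Clavien Dindo threshold, with no rule for grading an event dealt with inside the index operation, so a reported zero would not show that none occurred

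*Protocol*

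**What the plan says.** Protocol section 11.2.2, item 4(vii), defines the outcome as "Incidence of intra-operative surgical complications, the proportion of patient participants experiencing" a Clavien Dindo grade above III. Item 4(viii) applies the same scale and threshold after surgery: "Incidence of postoperative surgical complications, the proportion of patient participants experiencing greater than grade III severity".

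Table D (section 12.4) sets out the scale. Grade 1 is "Any deviation from the normal postoperative course without the need for pharmacological treatment or surgical, endoscopic and radiological interventions". Grades 2 to 4 are set by the treatment or level of care required; grade 3a, for example, is "Requiring surgical, endoscopic or radiological intervention – not under general anaesthesia", and 3b is its counterpart under general anaesthesia. Grade 5 is death.

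The protocol means to cover events during the operation. Objective 5 (section 2.3) includes intra-operative safety. Section 12.7.2 starts the reporting period at knife to skin, and section 12.8.3 defines an intra-operative category running until the dressing is on. Table C, item 5, labelled as intra-operative, begins "Fracture around joint including femoral shaft perforation or fracture, calcar fracture, trochanteric fracture" and goes on to acetabular fracture or perforation.

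The grade also controls what is collected. Section 12.8.1 says "Any AESI with a severity grade of 3 or higher is to be recorded on the Adverse Events CRF". Section 12.3 makes AESIs reportable to the trials centre at the same grade and otherwise requires only serious device-related events.

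**The concern.** A complication that arises and is put right in one operation may leave the post-operative course unchanged. Table D does not say whether it should then be graded by that normal course or by the surgical treatment it needed in theatre. Both readings can be defended from the text, and they fall on opposite sides of the CRF threshold.

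Two things are at stake. Sites may record the same event differently. And the figure offered for intra-operative safety could be zero because there were no events, or because none was graded high enough. For a feasibility study meant to inform a larger trial, that zero cannot be used. A later analysis plan cannot repair it, because events kept off the CRF cannot be recovered at analysis.

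The acetabular part of item 5 matters most. Section 2.1 describes both arms as having a cemented stem, so the randomised contrast is the fixation of the socket.

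**Working it through.** The protocol gives no complication rate, so there is no figure to reproduce. The check sets the rules side by side and then counts.

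**Inputs.** 40 participants, 1:1 (section 4.1), so about 20 per arm; outcome cut-off above grade III (11.2.2); CRF and reporting cut-off grade 3 or higher (12.3, 12.8.1); grade definitions (Table D).

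**Step 1: one event through the rules.** Take an acetabular fracture fixed in the same operation, followed by a normal recovery.

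| Reading of Table D | Grade | On Adverse Events CRF? | In 4(vii) as written? | In 4(vii) if the cut-off were grade 3 or higher? |
|---|---|---|---|---|
| Post-operative course was normal | none or 1 | no | no | no |
| Needed surgical intervention | 3a or 3b | yes | no | yes |

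Nothing in the protocol chooses between the rows. The choice decides whether the event is captured. Under the literal cut-off it does not change 4(vii), which excludes the event either way.

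**Step 2: the count.** Let k participants have such an event.

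- 4(vii) as written: 0/40 under both readings.
- Cut-off read as grade 3 or higher: 0/40 or k/40. For k = 1, 2, 3 that is 1/40 = 2.5%, 2/40 = 5.0%, 3/40 = 7.5%. Within an arm, one event is 1/20 = 5%.
- Count by event type with no grade threshold: k/40, whatever grade is assigned.

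**Step 3: what a reported zero would convey.** The exact 95% interval for 0/40 is 0 to 8.8%. If two participants had in fact had such an event, the count by type would be 2/40 = 5.0%, exact 95% interval 0.6% to 16.9%.

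**Step 4: how likely the problem is to arise.** The true rate p is an assumption. Expected events are 40p, and P(at least one) = 1 − (1 − p)^40.

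| Assumed p | Expected in 40 | P(at least one) |
|---|---|---|
| 1% | 0.4 | 0.33 |
| 2% | 0.8 | 0.55 |
| 5% | 2.0 | 0.87 |
| 10% | 4.0 | 0.98 |

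**The case against.** The strongest reply is that the scale can be applied. Only grade 1 mentions the post-operative course, and grade 3 simply asks whether surgical intervention was needed. A reader might infer that Clavien Dindo has no place at all for intra-operative events; Table D does not support that. What is missing is a rule for choosing between the two readings.

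A reader might also infer that reported incidence swings by 2.5 or 5 points between sites. Under the literal cut-off it does not, since both readings give 0/40. The swing needs a cut-off of grade 3 or higher. Nor does the 3a/3b split, which would follow the index anaesthetic, affect any count: no rule separates the two.

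It is tempting to add that cross-over information is lost. It is not: item 4(vi) counts cross-over without a grade filter, and section 7.4 collects changes of implant type. Only the link from complication to cross-over is at risk. The femoral events in item 5 also say little about a difference between arms that share a cemented stem.

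Other records exist. Serious device-related events are reportable whatever their grade, and section 12.7.1 keeps serious and routinely recorded events in the notes. Section 7.4 collects safety data on the day of surgery but refers to section 12 for the reporting rules. Section 7.5 collects AESIs at six weeks without naming a grade, though its examples are post-operative. Section 12.8 defers detail to a Safety Plan not seen here. Such events therefore need not disappear from every record, but none of these routes is stated to feed 4(vii) free of the grade filter.

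Finally, section 12.3 limits safety recording on purpose, and the numerical stop/go criteria in section 11.5 concern recruitment only. That limits the importance of the point without removing it.

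**Conclusion.** The point holds as a gap in the outcome definition and in data capture. Followed as written, the protocol lets an intra-operative fracture or perforation fixed in the same operation be recorded at one site and not at another. Read literally, it leaves that event out of 4(vii) unless it leads to a grade 4 or 5 outcome. A reported 0/40 would therefore not show that such events were absent.

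The size cannot be fixed from the protocol: each event is 1/40 overall and about 1/20 in an arm, and the number of events is unknown. The conclusion rests on two assumptions: that at least one such event occurs, and that the Safety Plan contains no grading rule that settles the matter. Safety is a secondary objective in this feasibility study, so this is a worthwhile, inexpensive correction and not a threat to the main feasibility conclusions.

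**What to change.** - In 11.2.2, define 4(vii) as the number and proportion of participants with any Table C event in the intra-operative timeframe of 12.8.3. List the events by type and by whether cross-over followed, with no Clavien Dindo threshold.
- In 12.3 and 12.8.1, require intra-operative AESIs on the Adverse Events CRF whatever their grade. This concerns recording only and adds no expedited reporting.
- Keep Clavien Dindo for post-operative complications in 4(viii), and reconcile the outcome cut-off (above grade III) with the reporting cut-off (grade 3 or higher). That mismatch is a separate matter: moving the cut-off alone would not settle how an event managed within the operation is graded.

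The cost is wording in three sections and a few extra CRF entries across 40 participants. The downside is a small widening of the deliberately limited safety recording in 12.3.
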